7.3 DISCONTINUATION OF PARTICIPATION

Discontinuation of treatments does not mean discontinuation from the study, and patients in XCELSIOR have the option of returning their case to the VTB process for new or additional options development if they experience side-effects or progress on a chosen therapy. Furthermore, for late-stage cancer patients, hospice is considered a likely option during the study. Patients are not considered discontinued or withdrawn from the study if they choose to receive hospice care. Patient information will be collected until death, unless the patient chooses to withdraw from the study. Patients are free to withdraw at any time by providing notice of withdrawal in writing using established procedures documented on the xCures Web site and including an option to provide a reason for withdrawal from the study. Withdrawal from the study means that no additional data will be collected on the patient (excluding public records searches to confirm dates of death) and does not constitute revocation of XCures acting alone or on behalf of a partner or collaborator right to use the data collected prior to withdrawal for the purposes described herein.

7.3.1 PARTICIPANT DISCONTINUATION/WITHDRAWAL FROM THE STUDY

XCures acting alone or on behalf of a partner or collaborator or their authorized designee may discontinue a participant or withdraw a participant from the XCELSIOR study for any reason at any time.

7.3.2 LOST TO FOLLOW-UP

As a patient advocate, XCures acting alone or on behalf of a partner or collaborator frequently contacts patients to share information and assist with discussions related to care, coverage, or responses to treatment. If a patient is unreachable, XCures acting alone or on behalf of a partner or collaborator may continue to attempt to contact the participant, their doctor (or other members of their treatment team), or their designated Emergency Contact by phone, email or similar method. Patients that are not reachable will be considered lost to additional follow-up. Patients that choose to receive hospice care, will not be contacted further. In either case, XCures acting alone or on behalf of a partner or designee may undertake public records search

7.4 VIRTUAL DATA MONITORING COMMITTEE

A subset of the VTB members will be designated as the virtual Data Monitoring Committee (vDMC), which will operate remotely and be charged with periodic review and discussion of safety and effectiveness signals within and among groups and subgroups of patients in the XCELSIOR registry. The vDMC will be empowered to make determinations about:

• adding or removing treatment options from additional consideration for subgroups, based on futility or harm—such determinations should be publicly reported through peer-review mechanisms promptly,

• treatment options for subgroups that no longer belong in an equipoise option set because they are clearly effective, such options may be graduated to other research endeavors, such as GBM-AGILE for randomized clinical trials, or may be the subject of analysis and publication to ensure dissemination to stakeholders.

The vDMC may identify safety signals which, while not altering treatment recommendations for a population subgroup, should be disseminated through publication and notification to clinicians, sponsors or manufactures, and the public. Related to this is information developed in support of mitigation or management strategies including supportive care recommendations identified in relation to adverse events assessed by the vDMC. The initial inclusion of potential options does not require approval by the vDMC and any treatment for which there is medically-logical evidence may be considered by the VTB members. The sequential review by the scientist, Medical Director, and VTB may provide independent adjudication of imaging or endpoints to supplement information reported by the patient or their physician or abstracted from their medical record.

7.4.1 SIGNAL DETECTION PROCESS AND SCHEMA

Signal detection activities will be based on composite endpoints, as well as outcomes in relation to a baseline trajectory forecast. Because patients with late-stage and recalcitrant cancers have no proven options and only a short time in which to explore options, XCELSIOR aims to rapidly assess signals of effectiveness and safety/tolerability through composite assessment of changes in direction, magnitude, or rate of change in labs, images, disease symptoms, patient functioning, side effects, and/or changes in pharmacotherapy. Analytic methods, including traditional methods and machine learning may be used to identify and assess changes in status, which will be combined with human expert judgment to evaluate and classify signals.

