7.2.1 TREATMENT SWITCHING

Since the purpose of this study is to develop information that supports personalized medicine in oncology, patients and their clinicians may switch or modify treatments in response to clinical outcomes. Treatment switching will be collected and mark an event for outcomes assessment purposes. The cause of treatment switching will be identified via discussion with the patient and their physician in order to code the reason for switching such as side-effects or lack of efficacy. The reason for treatment discontinuation or switching will be

recorded in the eCRF. Patients that switch treatments may request that their case be reassessed through the VTB process.

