8.1.4 ANALYTIC SIGNAL DETECTION

General and disease-specific response signals will be detected using traditional query detection methods augmented with both human expertise and machine learning techniques. Signals will be detected by monitoring routine and spontaneous assessments collected from the medical record and augmented with surveys, which may include labs, imaging, patient- and physician-reported questionnaires, and other information such as treatment switching or progression declarations. Signals may be detected from changes in magnitude or rate of change and scored based on direction of the change and correlation with the VTB treatment rationale. Once detected, potential signals will be escalated for human review by a scientist, medical director, or the VTB/vDMC. Signals may be mapped to response criteria, for example RANO. Spontaneous response measures, such as time-to-progression, time-to-treatment switching, and/or changes to anti-cancer therapy regimen will be detected and scored using paired TTP or TTTS and in relation to baseline forecasts.

It should be noted that signal detection in non-linear networked systems, such as the composite responder analysis integrating numerous non-linear assessments into a network of aggregated n-of-1 experiments, benefits from a certain level of "noise" within the network. This phenomenon is called stochastic resonance and is widely used in telecommunications and other networked systems to amplify weak signals in a noisy environment. Such approaches may be considered for enhancing signal detection in XCELSIOR.

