8.1.7 STATISTICAL ANALYSES

Because the symptoms of recalcitrant cancers can be diverse, an integrated responder analysis approach will be used for signal detection. This approach will integrate symptomatic, clinical, laboratory, imaging, or other measures of response into a responder analysis framework. This approach has been used successfully in rare disease studies that are characterized by few patients and diverse symptoms.

Because individuals in XCLESIOR are likely to have few treatment opportunities due to a short expected lifespan, the goal of responder analysis is to identify response early, or in the absence of response work with the patient, their physician and the VTB to try the next equipoise option or re-run the VTB process quickly to start an alternative therapy. This approach should enable XCELSIOR to observe a series of n-of-1 treatments within patients. These changes occur naturalistically during the treatment of cancer patients and will be evaluated individually and in an aggregated n-of-1 analysis for safety and effectiveness signal detection. Effectiveness signal detection may be based on Bayesian models that incorporate hierarchical clustering with additive regression trees to both group patients in a continuously learning model, while also implementing a flexible and efficient model layer for estimating individual treatment response prospectively using Bayesian Additive Regression Trees (Logan et al., 2018).

Analyses may be conducted to assess hypotheses for both the safety and/or effectiveness of various treatments along or in combination for different patient subgroups, based on the emergence of data suggesting new hypotheses. VTB members and interested researchers may propose research plans and analyses to XCures acting alone, on behalf of, or with partner or collaborator. Such analyses will be reviewed by XCures acting alone, on behalf of, or with partner or collaborator and may be undertaken in accordance with the publication policy in Section 5.1.7.

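### Change-based effectiveness signals are scored by direction with no stated correction for lines that start after a poor reading, so regression to the mean can appear as response

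*Protocol*

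**What the plan says.** Protocol 7.4.1 names two bases for signals: "Signal detection activities will be based on composite endpoints, as well as outcomes in relation to a baseline trajectory forecast". It then describes the composite as an assessment of "changes in direction, magnitude, or rate of change in labs, images, disease symptoms, patient functioning, side effects, and/or changes in pharmacotherapy".

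Protocol 8.1.4 gives the scoring: "Signals may be detected from changes in magnitude or rate of change and scored based on direction of the change", and also on how well the change agrees with the tumor board's rationale. A separate sentence covers time to progression, time to treatment switching and regimen changes; these "will be detected and scored using paired TTP or TTTS and in relation to baseline forecasts". The change-based sentence has no such link. Afterwards, "potential signals will be escalated for human review by a scientist, medical director, or the VTB/vDMC".

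On how lines begin, 7.2.1 says that "patients and their clinicians may switch or modify treatments in response to clinical outcomes", and that staff will "code the reason for switching such as side-effects or lack of efficacy". Section 7.3 lets patients return to the tumor board after side-effects or progression. Section 8.1.7 moves non-responders quickly to the next option and says that "the goal of responder analysis is to identify response early".

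The forecast is the trajectory of the patient's cluster, computed as a registration step (5.1.1.1, step 6); 8.1.1 likewise places it at enrollment.

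**The concern.** If a line starts because a fluctuating measure has just looked bad, the reading at the start is partly an unlucky one. Later readings tend to fall back towards the patient's usual course, and the slope leading into the start is too steep. Scoring the direction of change across that point then credits the new treatment with some of the rebound.

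The error has a consistent sign, so pooling many n-of-1 results makes it more precise rather than smaller. It grows with the noise of the measure, so it can distort rankings between options as well as their level. The efficacy signal enters the Leaderboard (8.1.2), which goes into the case material for later patients (5.2.2). The vDMC may judge an option clearly effective and take it out of equipoise (7.4).

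**Working it through.** **Inputs.** The protocol states no threshold, test-retest correlation, visit spacing or rate of worsening, so there is no figure to reproduce. Every size below rests on assumed values.

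**1. Marker simulation.** Monthly log marker y(t) = b·t + e(t), with e(t) normal with SD s, no treatment effect, and 40,000 patients per setting. A line starts at the first t ≥ 4 where y(t) minus the lowest earlier value is at least ln 1.25 = 0.223. Slope before = [y(t) − y(t−2)]/2; slope after = [y(t+2) − y(t)]/2. The unselected comparison applies the same sums at a visit not chosen for its value. Base case: b = 0.05, s = 0.15.

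| Base case | After a poor reading | Unselected |
|---|---|---|
| Slope lower after than before | 70% | 50% |
| Rise then fall between adjacent readings: y(t) > y(t−1) and y(t+1) < y(t) | 48% | 32% |

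The mean slope appears to drop from 9.6% to 1.4% a month, while the true value stays at 5%. The excess in rise-then-fall is 48 − 32 = 16 points. At s = 10%, 15% and 20% the apparent drop in slope is about 6, 8 and 10 points.

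Over b = 0–10% and s = 10–20%, the share with a lower slope runs from 53% to 95%. At b = 10% it is only 53–57%, because fast true progression triggers most starts and leaves little to regress.

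**2. Closed form.** For a standardized measure with test-retest correlation ρ and selection above cut-off c, the expected apparent improvement is (1 − ρ)·φ(c)/[1 − Φ(c)] SD. For the worst 25%, c = 0.674 and φ(c)/0.25 = 0.318/0.25 = 1.27. At ρ = 0.8 this gives 0.2 × 1.27 = 0.25 SD; at ρ = 0.7, 0.38 SD; at ρ = 0.9, 0.13 SD.

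Share improving by at least 0.5 SD with no effect and no drift, unselected then selected:
- ρ = 0.7: 26% and 43%
- ρ = 0.8: 22% and 34%
- ρ = 0.9: 13% and 20%

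With true worsening of 0.25 SD per interval at ρ = 0.8, the mean change is about zero, yet the share is still 21% against 12%. With 0.5 SD, the mean change is −0.25 SD and the share is 11% against 6%.

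**3. Which corrections work** (no treatment effect throughout)
- *Forecast conditioned on the value at line start:* mean spurious improvement within 0.01 SD of zero; 20% cross 0.5 SD at ρ = 0.8, close to the 22% unselected.
- *Observed value plus an average slope:* the full 0.25 SD remains at ρ = 0.8.
- *Cluster mean not conditioned on the patient's value:* about 1.0 SD against the new line in the closed-form model, where patients differ persistently. In the marker simulation, where the forecast line is correct for each patient, it is unbiased (50% below the line).
- *Dropping the triggering reading from both slopes:* 43% show a lower slope in the base case, and under 50% in every setting. The base-case slope goes from about 2.6% before to 5.0% after, so an inert option looks harmful. If two consecutive high readings are needed to start a line, 56–75% still show a lower slope.
- *Requiring two agreeing readings:* 29% confirmed against 20% unselected, when the triggering reading is the reference.
- *Comparing lines with the same trigger:* both sides carry the same expected rebound when the triggers and noise are alike, so it cancels in the comparison.

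**The case against.** The strongest reply is that the protocol fixes little here. Sections 7.4.1 and 8.1.4 set no reference reading, 8.1.4 is worded permissively and allows mapping to formal response criteria, and a baseline window or confirmation rule could sit in an SAP that is not shown. That stands as far as the missing detail goes. It does not cover the scoring rule, which the protocol does state: direction of change plus fit with the rationale, with no forecast attached.

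The protocol also has comparators. Section 3 says outcomes for specific treatments may use durable response against historical controls or prospective forecasts, 2.2.9 uses forecasts and progression-time ratios as internal controls, and 7.4 allows independent adjudication of imaging or endpoints. So a reader who inferred that there is no comparator at all would be wrong. But these are optional, and the forecast is not said to be conditioned on the values at a line start.

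A reader might also infer that every line starts because the measured values worsened. The text does not support that: 7.2.1 and 7.3 both give side-effects as a reason. Nor is the 48% a false-response rate. The unselected figure is 32%, the result depends on using adjacent readings (the two-interval slopes give about 40%), and a change of direction is not a clinical response. In the base case, a fall of at least 30% two readings after the start occurs in about 2% of lines.

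**Conclusion.** The concern holds in a limited form. The change-based route, as written, has no protection against regression to the mean, and lines are often started in circumstances that produce it. Fluctuating measures such as symptoms, function, quality of life and laboratory values can therefore show apparent response on an inert treatment, and aggregation does not cure it.

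In the settings examined, selection raised the share of apparent improvers, but its size cannot be derived from the protocol. It may be large (70% against 50% in the base case) or small (53–57% where progression is fast), and true worsening can cancel or exceed the regression in the mean change. The documents do not support the stronger inference that observed signals would be mainly artefact, or that the forecast-based route shares this bias. This is a point the sponsor should address in the analysis wording; it does not call the registry's data collection into question.

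**What to change.** Amend Protocol 7.4.1 and 8.1.4. In the aggregated analysis and the Leaderboard, and before the vDMC treats an option as clearly effective, compare each option's change-based signal rate with one of:

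1. the rate in lines of other options that were started for the same coded switch reason and after similar preceding worsening; or
2. a forecast updated at line start and conditioned on the values up to and including the triggering reading.

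A two-reading confirmed signal may be reported as a supplement, but should not be presented as correcting the bias. Dropping the triggering reading should not be the correction, because it can reverse the bias. Unconfirmed signals still go to human review at once, so early reading is kept.

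The cost is modest: the switch reasons and readings are already to be collected, so this is a change of wording and some extra analysis. Comparisons will be less precise where few similarly triggered lines exist.

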7.4.2 QUALIFICATIONS AND TERM FOR VDMC MEMBERS

Members of the vDMC will be drawn from the VTB supplemented with appropriately qualified individuals representing patients or advocates; clinicians; statistical or data scientists; pharmacologists; molecular, cancer or systems biologists; and others, as needed to fulfil the vDMC oversight function. Members of should be free of conflict of interest, or measures should be in place to minimize perceived conflict of interest. The vDMC will meet at least semiannually to assess safety and efficacy data and will operate under the rules of an approved charter or SOP, that will include keeping of written meeting minutes of deliberations. Members will serve a two-year term of service, which may be renewed indefinitely and must comply with the conflict-of-interest policy.

7.5 Adverse Events and Serious Adverse Events

7.5.1 DEFINITION OF ADVERSE EVENTS (AE)

The XCELSIOR registry is not a treatment protocol, it is a non-interventional registry study. However, to facilitate the generation of real-world evidence for the effectiveness and safety of cancer treatment regimens, information about spontaneously reported adverse events or events identified through the processing of the patient medical or health records will be identified analytically based on the emergence of the event in relation

to its presence or absence in the medical record at prior time points. Events may also be reported directly by the patient or their physician using surveys or directly through correspondence with XCures acting alone or on behalf of a partner or collaborator and/or xCures. In such cases, reasonable efforts will be made to gather information about the event.

Adverse events will mean any untoward medical occurrence associated with the use of an intervention whether or not considered intervention-related (21 CFR 312.32 (a)). Coding of AEs will be based on the CTEP dictionary (https://ctep.cancer.gov/protocolDevelopment/codes_values.htm#disease)and the severity of AEs will be graded based on CTCAE (https://ctep.cancer.gov/protocolDevelopment/electronic_applications/ctc.htm). In both cases, reasonable efforts will be made to code the events in accordance with standard dictionaries if the information is available directly or by imputation.

The primary focus of the Research Data will be on treatment-emergent events that meet the CTCAE criteria of Grade 3 or higher, therefore these events will be captured and assessed in the registry database to the extent possible. Assessment and analysis will focus on identifying treatment-emergent adverse events in relation to anti-cancer treatments identified within the patient's medical record, particularly those related to dose modification or interruption of anti-cancer therapies, or other therapeutic intervention or modification, including hospitalization or other medical treatment. Discontinuation of therapy due to lack of efficacy will be treated as a therapeutic outcome not an Adverse Event.

7.5.2 DEFINITION OF SERIOUS ADVERSE EVENTS (SAE)

In order to enable comparison with conventional clinical trial databases and to provide real-world evidence about the effectiveness and safety of anti-cancer treatments, XCELSIOR will capture serious adverse event information, when AEs within the medical record (or reported by the patient or their physician) appear to meet the criteria for seriousness, if, in the view of either the patient's physician, the event results in any of the following outcomes: death, a life-threatening adverse event, inpatient hospitalization or prolongation of existing hospitalization, a persistent or significant incapacity or substantial disruption of the ability to conduct normal life functions, or a congenital anomaly/birth defect. Important medical events that may not result in death, be life-threatening, or require hospitalization may be considered serious when, based upon appropriate medical judgment, they may jeopardize the participant and may require medical or surgical intervention to prevent one of the outcomes listed in this definition.

7.5.3 RELATIONSHIP TO UNDERLYING DISEASE OR TREATMENT

Adverse events that meet the tracking criteria (CTCAE 3 or higher and are treatment-emergent) will have relationship to the patient's underlying disease or treatment assessed if that assessment is available from the patient's physician and coded to the following rubric:

- Definitely Related
- Probably Related
- Possibly Related
- Unlikely to be related
- Not Related

Relationship to the treatment or underlying disease will be captured in the Research Data. Physicians may be queried directly for this information. The final determination will be made using the Signal Detection process and can include input from the patient, their physician, information from the medical record, and review and discussion by XCures acting alone or with partner or collaborator personnel and the VTB/vDMC members.

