3 OBJECTIVES AND ENDPOINTS

The primary objective of XCELSIOR is to collect data into a registry that enables the implementation of a patientcentered, AI-enhanced learning model for optimizing treatment selection in precision oncology. This includes necessary activities to support creation of that model, including processes, tools, and systems to support patient options, including the VTB, including insight capture and analysis of VTB recommendations and physician treatment selection, as well as improving patient access to precision medicine tests and therapies, and collection of associated information with patient safety and effectiveness outcomes in a longitudinal, observation data registry.

Secondary objectives include measurements of safety, tolerability, and effectiveness of therapies measured using outcomes and endpoints derived from RWE supplemented with patient or physician surveys and tracked at the individual patient level and used for aggregated n-of-1 analyses. Patient endpoints will include responder analysis using a composite of clinical response rates measured through disease- or therapy-relevant laboratory changes (e.g., CA19-9 for pancreatic adenocarcinoma), symptomatic improvement, health-related quality-of-life changes, functional performance, therapeutic switching, and radiographic response. Outcomes for specific treatments may be based on, as appropriate, time-to-treatment-switching and/or time-to-progression ratios, as well as response rates measured using durable response relative to historical controls or in relation to prospective forecasts. Additional secondary endpoints may be assessed for comparative effectiveness in relation to traditional clinical trials, including progression free survival at various time points, high-grade complications (SAEs or CTCAE v5.0 grade 3 or higher events)

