7.5.4 EXPECTEDNESS

Adverse events that meet the tracking criteria (CTCAE 3 or higher and are treatment-emergent) and are thought to be treatment-related will be assessed against known information for the treatment and then assessed for expectedness. Events are considered unexpected if the nature, severity, or frequency of the event is not consistent with the risk information previously described for the treatment. Physicians may be queried directly for this information. The final determination will be made using the Signal Detection process and can include input from the patient, their physician, information from the medical record, and review and discussion by XCures acting alone, on behalf of, or with partner or collaborator personnel and the VTB/vDMC members.

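### Relatedness and expectedness are gated on CTCAE Grade 3 or higher, so the protocol provides neither judgement for a treatment-emergent SAE that is captured but graded below 3 or cannot be graded

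*Protocol*

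**What the plan says.** Four places in the protocol bear on this.

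- **Section 7.5.1** sets the general emphasis: "The primary focus of the Research Data will be on treatment-emergent events that meet the CTCAE criteria of Grade 3 or higher". It also promises reasonable efforts, not certainty, in coding events, depending on whether the information is available or can be imputed.
- **Section 7.5.2** adds a second route that depends on seriousness and not on grade: "XCELSIOR will capture serious adverse event information, when AEs within the medical record" appear to meet the listed outcomes. It extends to medically important events: "Important medical events that may not result in death, be life-threatening, or require hospitalization may be considered serious". One stated reason for capturing SAEs is comparison with conventional clinical trial databases.
- **Section 7.5.3** opens the relatedness step with "Adverse events that meet the tracking criteria (CTCAE 3 or higher and are treatment-emergent", and makes the assessment conditional: "if that assessment is available from the patient's physician and coded to the following rubric".
- **Section 7.5.4** opens the expectedness step with the same gate and one further condition: "Adverse events that meet the tracking criteria (CTCAE 3 or higher and are treatment-emergent) and are thought to be treatment-related".

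Section 3, among the additional secondary endpoints that may be assessed, lists "high-grade complications (SAEs or CTCAE v5.0 grade 3 or higher events". Seriousness and grade stand there as alternatives.

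**The concern.** Seriousness and severity grade are different scales. The protocol recognises this in 7.5.2, where grade plays no part in the definition of an SAE, and in section 3, where the two are joined by *or*. The two sections that govern causal and expectedness judgements use grade alone, together with treatment emergence. A treatment-emergent SAE below Grade 3 thus enters the database through one rule and falls outside the next two.

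What is at stake is the completeness of the safety evidence. A reader comparing this registry with a conventional trial database would naturally look for related SAEs and unexpected SAEs. Under the present wording those tables would be limited to SAEs of Grade 3 or higher, without saying so. That undercuts the purpose that 7.5.2 gives for collecting SAEs.

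**Working it through.** The protocol states no figure on this point and no arithmetic applies. The check is to set the rules side by side, follow each kind of event through them, and then look for a rule elsewhere that closes the gap.

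**Conditions for each step**

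1. SAE capture (7.5.2): meets a seriousness criterion. No grade condition.
2. Relatedness (7.5.3): Grade 3 or higher, and treatment-emergent, and the physician's assessment is available.
3. Expectedness (7.5.4): Grade 3 or higher, and treatment-emergent, and thought to be treatment-related.
4. All-cause count (section 3, optional): SAE, or Grade 3 or higher.

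**What happens to each kind of event**

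| Event | Captured | Section 3 count | Relatedness step | Expectedness step |
|---|---|---|---|---|
| SAE, Grade 3 or higher, treatment-emergent | yes | can be counted | yes, if physician's assessment available | yes, if thought related |
| Non-serious, Grade 3 or higher, treatment-emergent | yes | can be counted | yes, same condition | yes, same condition |
| SAE, Grade 1 or 2, treatment-emergent | yes | can be counted | not provided for | not provided for |
| SAE, grade not established, treatment-emergent | yes | can be counted | not provided for: the criterion cannot be shown to be met | not provided for, same reason |
| SAE, any grade, not treatment-emergent | yes | can be counted | not provided for | not provided for |

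Rows three and four are the gap. The last row is also outside the gate, but because of the treatment-emergence condition, which is not disputed here. Row one shows that passing the grade gate is not enough by itself: the physician's assessment must also be available for relatedness, and the event must be thought related for expectedness.

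**Search for a rule elsewhere**

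- Sections 7.4 and 7.4.1 (virtual Data Monitoring Committee, signal detection) and 8.1.4 (analytic signal detection) describe review of safety signals without a grade limit. None of them requires a relatedness or expectedness classification for an SAE below Grade 3.
- Sections 7.5.3 and 7.5.4 send the final determination to the signal detection process, but within sections whose opening sentence has already limited them to events that pass the gate.
- Section 7.5.5 permits reporting of adverse events and adds no assessment step.
- Section 7.6.1 concerns unanticipated problems and asks about relation to the research, not to the anti-cancer treatment.

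No section extends either judgement to the events in rows three and four.

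**The case against.** The best defence is that the gate is a declared scope choice in a non-interventional registry. Section 7.5.1 says where the emphasis lies, the synopsis lists Grade 3 or worse events among its safety endpoints, and section 7.2 uses the same threshold when collecting treatment given for adverse events. Sections 7.5.3 and 7.5.4 are consistent with that. The defence explains where the threshold comes from. It does not explain why 7.5.2 then collects SAEs of any grade for comparison with trial databases and leaves some of them without the two judgements such a comparison would commonly use.

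Four stronger readings are tempting, and the document does not support them.

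- *That the gate contradicts the section 3 endpoint.* It does not. Section 3 describes an optional count of events from any cause and mentions neither relatedness nor expectedness. A low-grade SAE can be counted there without a causality code. Section 3 matters here only because it shows that the protocol regards seriousness and grade as separate routes.
- *That safety signal detection rests on these two steps.* The dependency runs the other way: both sections refer the final determination to signal detection, which draws on a wide range of inputs with no grade limit.
- *That such an SAE can never receive a causality judgement.* Nothing forbids one, and expert review may reach the event. Section 7.5.1 also directs attention to events that lead to hospitalisation or a change of therapy, in a sentence with no grade limit of its own. The accurate statement is that the protocol provides for no such judgement.
- *That a reporting duty fails.* Section 7.5.5 is permissive and does not depend on relatedness or expectedness, and unanticipated problems have a separate test.

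It is also fair to say that many SAEs may be Grade 3 or higher anyway, so the gap could be small.

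**Conclusion.** The point holds as a limited defect in a stated rule. Treatment-emergent SAEs graded below 3, or not gradable from the record, are captured, but the protocol gives no route to a relatedness or expectedness judgement for them. A tabulation of related or unexpected SAEs built on 7.5.3 and 7.5.4 would leave them out and so be incomplete. The all-cause count in section 3 and the general signal review are not affected.

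The size cannot be stated. The protocol gives neither an SAE rate nor the share of SAEs below Grade 3, and the overlap between serious and Grade 3 or higher could be nearly complete. The conclusion does not depend on that share. It rests only on reading the parenthesis in 7.5.3 and 7.5.4 as the definition of the tracking criteria, which is how both sections use it. The consequence is incomplete safety evidence, not a failure of participant protection. The correction is worth making because it is small and serves the comparison that 7.5.2 says it wants.

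**What to change.** In sections 7.5.3 and 7.5.4, define the tracking criteria as treatment-emergent events that are CTCAE Grade 3 or higher **or** that meet the SAE definition in section 7.5.2. Keep the existing condition in 7.5.3 that the physician's assessment be available, and the condition in 7.5.4 that the event be thought treatment-related. The seriousness route also covers SAEs whose grade cannot be established.

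The change is one phrase in two sections and uses the review process already described. The cost is some additional abstraction and causality review, in an amount the protocol does not allow one to estimate. If the sponsor does intend the grade-only gate, 7.5.2 should say that SAEs below Grade 3 are captured without these assessments, and any table of related or unexpected SAEs should carry that limitation.
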